6.4 Methods and Timing of Assessing, Recording and Analyzing Variables

Data capture and management are described in detail in the Data Management Plan.

List and structure of individual eCRFs are also given in the Data Management Plan.

Data monitoring procedures are described in detail in the study's Monitoring plan.

The study will rely to a large degree on electronic data capture methods.

6.4.1 Types of Data

Overall, data collected in the course of the study may be divided into three categories:

1. captured by clinical personnel. This includes demographic characteristics, baseline migraine parameters, end of study questionnaires, adverse events reports. Source data may be paper worksheets, further transferred into eCRFs maintained by the EDC system.
2. patient reported outcomes. This includes feedback entered via the smartphone application regarding migraine pain level, migraine symptoms, treatment perception, rescue medications. These data are used for calculation of study endpoints. Here, source data will be electronic, followed by automatic transfer to eCRFs.
3. additional information and technical data, captured by means of a system of log files by the Application. This includes stimulation activation times, applied stimulation intensity, device defects information, and other.

6.4.2 Clinical Study Variables and Data Capture Tools

This section provides an overview of collected PRO data and its capture tools.

6.4.2.1 Start attack/episode PRO feedback data

The screen provides for collection of the following data:

Item	Description	Control type	Values range
Current migraine pain level	Current migraine pain level in pain grade categories	Dropdown list	Mild (1), Moderate (2), Severe (3).

Time from onset of migraine pain	Time from onset of migraine pain	Dropdown list	under 10 minutes 10-20 minutes 20-60 minutes 1-2 hours 2-4 hours over 4 hours
Nausea	Presence of nausea	Radio buttons	Y/N
Sensitivity to light	Presence of photophobia	Radio buttons	Y/N
Sensitivity to sound	Presence of phonophobia	Radio buttons	Y/N
Increased skin sensation	Presence of allodynia	Radio buttons	Y/N

6.4.2.2 2h PRO

This feedback dialog appears 2h after the treatment program has started.

The screen provides for collection of the following data:

Item	Description	Control type	Values range
Current migraine pain level	Current migraine pain level in pain grade categories	Dropdown list	No pain (0), Mild (1), Moderate (2), Severe (3).
Medication	Whether rescue medication was taken	Radio buttons	Y/N
Medication name	Rescue medication	Dropdown list	From a pre-defined list
Nausea	Presence of nausea	Radio buttons	Y/N
Sensitivity to light	Presence of photophobia	Radio buttons	Y/N
Sensitivity to sound	Presence of phonophobia	Radio buttons	Y/N

Increased skin sensation	Presence of allodynia	Radio buttons	Y/N
Arm side where device was applied	Left or right arm	Radio buttons	L/R
Pain location (side)		Dropdown list	L R both
Additional feedback	Additional, free style feedback	Textbox	Free text, optional

6.4.2.3 48h PRO

The screen shall provide for collection of the following data:

Item	Description	Control type	Values range
Current migraine pain level	Current migraine pain level in pain grade categories	Dropdown list	No pain (0), Mild (1), Moderate (2), Severe (3).
Medication	Whether rescue medication was taken	Radio buttons	Y/N
Medication name	Rescue medication	Dropdown list	From a pre-defined list
Additional feedback	Additional, free style feedback	Textbox	Free text, optional

6.4.3 *Methods and Timing of Assessing, Recording and Analyzing Variables*

Once the last patient will have completed the study and all the queries have been resolved, database will be locked, cleaned and exported for final statistical analysis. Study report will be issued following final database lock.

Recurrent treatments within 46 hours from first treatment of an attack are allowed, and are collected and analyzed as exploratory data. Use of rescue medication within the 48 hours from start of 1st treatment of the attack is considered a failure for sustained relief assessment.

6.4.4 Data Flow and Management

Data management function will be supported by a cloud based EDC system developed by Clear Clinica (Modi'in, Israel). Clear Clinica provides services for collection and remote monitoring of clinical trials data, compliant with HIPAA and 21 CFR Part 11.

EDC portals with secure authorized access will be made available to every participating site, as well as to the study monitor.

Data captured by clinical personnel will be entered directly into pre-specified eCRF screens by site personnel. Data from paper sources will be entered into the study database. Automatic data checks will be implemented for majority of entry fields to provide opportunity for resolving data inconsistencies as close as possible to real time. Effort will be made to identify missing or incorrect data and resolve the issues promptly.

Data collected onto the smartphone application will be directed to a secure cloud based database where it will undergo analysis aimed at detection of missing data and other inconsistencies. The smart phone will transmit PRO and technical data containing activation times, stimulation intensity and ePRO via the smartphone to a central electronic database for analysis. Activities such as repeatedly aborted programs, missing feedbacks, inconsistent stimulation intensity adjustments, and similar, will be communicated to research coordinator of the corresponding site, using participants' ID codes. Automated means were developed to identify and provide corresponding notifications regarding events that may lead to protocol deviations and/or missing data, and which resolution may require involvement of study staff. Examples of such events include missing PRO data or low device battery level. An automated system was implemented to notify the participant, site study coordinator and Sponsor study monitor on the above events. Missing data will be identified automatically by a script running on Clear Clinica's cloud, and queries will be generated to participants and corresponding site study coordinator. Near real time detection of problems in accumulating data will allow timely generation and resolution of queries. Intermediate data processing and translation into eCRF format are performed at this stage. Processed data are further pushed into the EDC system.

Schematics of data flow are presented in **Figure 5**.

[figure not shown]

Figure 5. Schematics of data flow

Back-up of the database is performed daily. In addition, copy of each participant's ePROs and other activity is stored in his/her smartphone memory and can be retrieved in case such need occurs.

Study database will be locked and exported using EDC tools into SAS compatible format for interim and final statistical analyses.

Query resolution will be performed using EDC tools.

All paper based source data and relevant medical documents meant to serve also as source documents will be maintained by the sites and available as eCRF attachments. Patient identification will be blackened from all data. Patients will be identified by their codes. The site investigator is responsible for ensuring that eCRFs are filled in a timely manner and relevant paper documents are properly stored. Investigator will provide the documents to the sponsor either through the sponsor representative or by mail per sponsor request.

Access to data will be authorized and controlled, in accordance with relevant laws and guidelines.

Study will be performed according to the protocol. At each site, the PI will appoint staff member(s) that will be responsible for completing the Case Report Forms supplied by the sponsor.

Specifics of data query handling are given in Data Management and Monitoring plans.

Audit trail for data entry and corrections will be maintained.

6.4.5 *Procedures for Review of Data*

A detailed description of data queries, their resolution and overall data flow can be found in the Data Management Plan.

Missing PRO data will be identified by a dedicated software running on the cloud closely to real time. Corresponding queries will be issued to study participants and site study coordinator. Effort will be made to resolve such queries as close as possible to real time.

6.4.6 *Data Monitoring Committee*

An independent Data Monitoring Committee (DMC) is charged with the task of providing regular oversight of the data monitoring issues as detailed in the document: "DMC". These experts will periodically review and evaluate the accumulated data for study progress. The DMC will make recommendations concerning continuation, modification, or termination of the study. The Data reviewed by the DMC will include a summary of the following topics:

- Study progress: Subject recruitment, comparison with targeted recruitment, retention, protocol adherence, and quality of data collection procedures.
- Treatment Monitoring: Data on treatment integrity and adherence.
- Safety Monitoring: Data related to the safety of the subjects, including any adverse events or side effects related to the treatment.
- Efficacy monitoring: Interim efficacy analysis is to be performed per algorithm presented in Section 7.5.
- Futility monitoring: Futility will be assessed at the time of interim analysis.

6.4.7 *Total Expected Duration of the Clinical Investigation*

The anticipated duration of the study is up to 18 months.

6.5 *Subjects*

6.5.1 *Inclusion Criteria*

Patients need to fulfill all the below Inclusion criteria:

1. Patient is 18-75 years old.
2. Patient meeting the ICHD-3 diagnostic criteria for migraine with and without aura
3. Patient reporting 2-8 migraine attacks per month.
4. Patient must be able and willing to comply with the protocol
5. Patient must be able and willing to provide written informed consent
6. Male or non-pregnant / non-lactating female (NOTE: Females of child bearing potential must have a negative pregnancy test and must be willing to use adequate contraceptive means during the study)
7. Possesses the basic cognitive and motor skills needed to operate android cell phone

6.5.2 *Exclusion Criteria*

Patients are excluded if they have any of the following:

1. Has other significant pain problem that in the opinion of the investigator may confound the study assessments
2. Is currently implanted with an electrical and/or neurostimulator device (e.g. cardiac pacemaker or defibrillator, vagus nerve neurostimulator, deep brain stimulator, spinal stimulator, bone growth stimulator, cochlear implant, Sphenopalatine ganglion stimulator or Occipital nerve stimulator).
3. Known uncontrolled epilepsy.
4. Use of Cannabis including medical use.
5. Has chronic migraine (more than 15 headache days per month).
6. Changed usage or dosage of migraine preventive medications in the last two months
7. Has undergone nerve block (occipital or other) in the head or neck within the last 2 weeks.
8. Is participating in any other clinical study.

6.5.3 *Contraindications*

Contraindications for the use of the Nerivio Migra device include those known for transcutaneous electrical stimulation procedures. In addition to restrictions described in exclusion criteria, Nerivio Migra shall not be placed over open wounds or burns, or on irritated skin.

The Nerivio Migra is **NOT** intended for use in any other location except the upper arm.

6.5.4 *Number of Subjects*

The total number of patients to be treated in this study is up to 248 eligible patients (see section 7.5).

6.5.5 *Expected Study Duration for Each Subject*

Study duration per patient is 4 complete treatment cycles and no longer than 3 months from enrollment (whichever is fulfilled sooner).

6.5.6 *Point of Enrollment*

Patients are formally enrolled in the study once they are found eligible by inclusion and exclusion criteria, have signed an informed consent and received training on the use of the device. If the patient was not treated with the investigational device, the patient will be excluded from the mITT data analysis set.

6.5.7 *Patient Withdrawal Criteria*

Patients may be withdrawn from the study by the PI or sponsor, if any one or more of the following events occur:

- The patient wishes to withdraw from the study without providing any explanation.
- Patient is lost to follow-up.
- Refusal of the patient to continue treatment and/or follow-up observations.
- Serious adverse event.
- Significant protocol deviation/violation or noncompliance, either on the part of the patient or investigator.
- Decision made by the investigator that termination is in the patient's best medical interest.
- Device failure.
- Other ethical or clinical considerations upon investigator discretion.

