Participants will be instructed to activate the device at onset of a qualifying migraine attack and manually adjust stimulation intensity to a level within the pre-defined range where it is well perceived but not painful. A qualifying migraine attack shall be preceded by at least 48 hours of freedom from headache. Patients will be requested to refrain from use of rescue medications prior to and during the first two hours after treatment with the device, and if they can not comply with this, record their use of rescue medications (migraine specific drugs or other medications or therapies that may be used to treat pain, from a pre-specified list) in the mobile application.

Via the smartphone application, each participant will be asked to rate his/her migraine pain level three times using Pain Grades Scale (0 - no pain, 1- mild pain, 2- moderate pain, 3 – severe pain): (1) upon starting the treatment, (2) two hours after start of treatment, (3) 48 hours after start of attack. At the start of each treatment, participants will be also asked to provide time elapsed from start of migraine attack to start of the treatment. Participants will be also asked to provide feedback regarding their use of medication (migraine specific drugs or other medications or therapies that may be used to treat pain, from a pre-specified list), presence of nausea, photophobia and phonophobia, and treatment perception. After providing feedback at two hours

after start of treatment and in case of pain recurrence, participants will be allowed to re-treat the attack using Migra device.

Adverse events will be reported.

Duration of study participation for each patient will be up to three months, determined by one month of the roll-in stage followed treatment of four qualifying attacks over the course of two months (whichever is achieved first).

Post study questionnaire will include patient global impression of change [27], blinding and usability assessments.

Stage Three. This part will include open label extended treatment. Following the completion of the study by all subjects and the return of all study devices, subjects will be offered a 2-month period of using active device, at no cost.

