6.2.2 Procedures to ensure blinding

This is a double-blind study: neither the patient, nor the investigators will be aware of arm allocation of each study participant. Maintaining double blind design is a known challenge in non-invasive neuromodulation devices trials. A number of means are planned to ensure the double blind aspect of this trial.

Selection of identically looking, active sham devices as control means is only a single step aimed at maintaining blindness. Each device will be numbered with 3 digit numbers, first digit site number and two digit subject numbers. Each new patient will be provided with d next consecutive numbered device.

Adherence to randomization procedure by clinical staff is critically important.

Importance of adherence to study design and procedures will be explained to participants in the course of enrollment.

No information regarding expected stimulation perception will be provided, except for the fact that stimulation intensity adjustment control will allow to adjust intensity to "a well perceived but non-painful" level.

In order to achieve blinding, participants will be trained individually. A training clip will be used for training, in order to minimize staff exposure to participants' reaction to and tolerability of treatment intensity.

In the course of the trial, participants will not be asked directly any questions regarding treatment perception.

The clinical staff will be instructed to not engage in any discussions regarding anticipated treatment perception.

End of study questionnaire will include individual blinding assessment to examine whether the blinding was well maintained throughout the study.

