6.6 Study related Procedures

6.6.1 General

The potential candidates will be screened to assess whether they are appropriate candidates for inclusion in this study. Informed consent will be obtained prior to initiation of any of the following clinical procedures that are performed solely for the purpose of determining eligibility for research. Pregnancy test for female patients with childbearing potential will be performed. The patient medical history, migraine history and diagnosis will be recorded and verified, the use of concomitant medication will be recorded in designated case report forms. Eligible patients will receive a documented training, and upon its successful completion the investigational device will be handed to study participants for home use. As per the IFU, participants are instructed to activate the device at the onset of a migraine headache and manually adjust stimulation intensity to a level where it is perceivable but not painful. Participants are requested to refrain from use of rescue medications prior to and during the first two hours after treatment and, if could not comply with this, record their use in the cellular application. Via the smartphone application, each participant will be asked to rate his/her migraine pain level three times: (1) upon starting the treatment, (2) two hours after treatment, (3) 48 hours after first treatment corresponding to the current migraine attack, using Pain Grades Scale (0 - no pain, 1- mild pain, 2- moderate pain, 3 – severe pain). At the end of each treatment, participants will be asked to provide feedback using the application regarding the time elapsed from start of migraine attack to start of the treatment, their use of medication. In case of failure to provide feedback regarding pain level post-treatment, telephone follow-up will be performed by study investigator staff to solicit such feedback. Additional migraine symptoms will be self-reported using the application. Follow up phone calls will be scheduled to record change in medical condition, concomitant medication and migraine therapy. Unscheduled visits will be recorded and termination visit will be scheduled upon the completion of the study as defined by treatment of four qualifying attacks over the course of two months (whichever is achieved first). In the event of premature discontinuation an early discontinuation visit will be scheduled.

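### Section 6.2.2 rules out direct questions on treatment perception, but 6.1 and 6.4.1 list it as app data, and nothing separates site staff who get device-use flags from those who phone for missing pain ratings

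*Combined protocol and SAP*

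**What the plan says.** Section 6.2.2 accepts that blinding is difficult for this kind of device and lists protections. Two matter here. First: "In the course of the trial, participants will not be asked directly any questions regarding treatment perception". Second, participants are trained one at a time with a video clip, to "minimize staff exposure to participants' reaction to and tolerability of treatment intensity"; that sentence is about the training session. Staff are also told not to discuss what the treatment is expected to feel like.

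Section 6.1 has participants give feedback through the app on medication use, "presence of nausea, photophobia and phonophobia, and treatment perception". Section 6.4.1 defines the patient-reported data as "feedback entered via the smartphone application regarding migraine pain level, migraine symptoms, treatment perception, rescue medications". Section 6.4.2 sets out the start, 2-hour and 48-hour screens item by item, and none contains a perception question.

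Section 6.4.4 deals with data reaching the cloud database: "Activities such as repeatedly aborted programs, missing feedbacks, inconsistent stimulation intensity adjustments, and similar, will be communicated to research coordinator" of the relevant site, by participant ID code. Where a post-treatment pain rating is missing, 6.6.1 says "telephone follow-up will be performed by study investigator staff to solicit such feedback"; the synopsis says the same. The 2-hour rating determines the primary endpoint (7.2.1).

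**The concern.** There are two separate problems.

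The first is textual. The document gives two answers on whether perception is collected during the trial. If the app were built from 6.1 and 6.4.1 rather than 6.4.2, participants would be prompted after each attack to think about what the stimulation felt like. That is what 6.2.2 sets out to avoid.

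The second is an unguarded route. How a participant adjusts intensity, and whether a program is stopped early, are behavioural signs of how the stimulation is felt. Section 6.2.2 limits that exposure at training; 6.4.4 allows a form of it throughout treatment. If someone who has seen such flags then phones for a missing pain rating, a guess about the arm could influence how a subjective 0-3 score is obtained. With four treated attacks, two pain-free ratings make a responder, so one phone-obtained rating can change a participant's status.

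**Working it through.** **Passages side by side**

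| Topic | One place | Another place | Relation |
|---|---|---|---|
| Perception during the trial | 6.2.2: not asked directly; 6.4.2: no such item | 6.1 and 6.4.1: listed as app feedback | Inconsistent; must be reconciled |
| Staff exposure to reactions to intensity | 6.2.2: minimized, at training | 6.4.4: abort and adjustment flags to the coordinator | No literal contradiction; works against the same aim |
| Alert recipient and caller | 6.4.4: research coordinator | Synopsis, 6.6.1: study investigator staff | May or may not be the same person; no separation stated |

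**Could a flag carry information about the arm?** Inputs are sham 0.1-0.5 Hz (6.1), active 100-120 Hz (Appendix A) and a 25-minute program (3.6), which is 25 × 60 = 1,500 s.

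- Sham: 1,500 × 0.1 = 150 to 1,500 × 0.5 = 750 pulses, or one every 10 to 2 seconds.
- Active: 1,500 × 100 = 150,000 to 1,500 × 120 = 180,000 pulses.
- Smallest rate ratio: 100 / 0.5 = 200.

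The arms should therefore feel different, and a sham user changing intensity may wait seconds for the next pulse. That makes arm-related adjustment behaviour plausible. It does not show that it occurs.

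**What would a bias do if it existed?** The plan gives no figure for this, so what follows is an illustration. Its base is the sample size in 7.4, which reproduces. With 30% v 10%, two-sided 5% and 80% power:

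n per arm = [1.96·√(2·0.20·0.80) + 0.8416·√(0.30·0.70 + 0.10·0.90)]² / 0.20² = (1.1087 + 0.4610)² / 0.04 = 61.6, so 62 per arm and 124 in total.

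Now assume no true effect (10% responders in both arms) and a reporting bias that raises the active responder rate. Exact binomial enumeration of the uncorrected two-sided chi-squared test gives the chance of p < 0.05:

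| Assumed bias (points) | 62 per arm | 124 per arm (maximum size, 7.5) |
|---|---|---|
| 0 | 5.1% | 5.0% |
| 2 | 6.4% | 7.9% |
| 5 | 12.9% | 22.2% |
| 10 | 33.6% | 61.0% |

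Five points is 0.05 × 62 = 3.1 participants in one arm, or 0.05 × 124 = 6.2 at the maximum size. The bias sizes and their direction are my assumptions; the documents supply none.

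**The case against.** The strongest reply is that nothing in 6.4.4 breaches 6.2.2. The exposure sentence speaks of minimizing, concerns training, and sets no rule on logged device use. Section 6.1 says sham pulses can be felt and their intensity manipulated much as in the active program, and 3.4 describes a mechanism that controls the speed of adjustment. It is unclear which arm an abort would point to: strong active stimulation and weak sham sensation could each cause one. The coordinator is not said to make the calls, nor are raw intensity values said to be sent. Some missing ratings may be recovered by the automated queries that go directly to participants. Access rules may also sit in the Data Management Plan or Monitoring Plan, which are separate documents. All of this stands, and it limits the point to an unguarded route rather than a demonstrated failure of blinding.

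It could also be said that an app item is not a direct question. That is a thin distinction, because 6.1 has participants asked for this feedback.

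A reader might infer from the pilot (complete reporting for 70% of P200 activations and 28% of placebo activations, Section 4.2) that phone-obtained ratings will fall mostly on sham. At 62 per arm and four attacks each, those rates would leave 62 × 4 × 0.30 = 74 active and 62 × 4 × 0.72 = 179 sham attacks incomplete. The documents do not support that step. The pilot was a cross-over that asked for four pain ratings per treatment, so an incomplete report need not mean a missing 2-hour rating. It already used telephone follow-up, and the text does not say whether the reporting rates count ratings recovered that way.

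**Conclusion.** Two things hold. The perception wording in 6.1 and 6.4.1 conflicts with 6.2.2 and with the screens in 6.4.2; that needs no assumption. Separately, abort and intensity-adjustment flags go to the site by participant code while site staff solicit missing ratings that feed the primary endpoint, and this document states no separation. That the flags could hint at the arm is an inference from the pulse rates.

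A reader might go further and conclude that site staff will be unblinded or that the primary result will be biased toward active. The documents contain no flag data by arm and do not name the callers, so neither conclusion is supported. The size and direction of any bias are unknown, and the illustration shows only that a shift of a few participants would matter if it occurred. This is an inexpensive improvement worth making, not a defect that invalidates the design.

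**What to change.** 1. Delete treatment perception from 6.1 and 6.4.1, so that they agree with 6.2.2 and the screens in 6.4.2. Keep the blinding assessment at end of study.
2. In 6.4.4, replace the abort and intensity-adjustment messages to sites with one neutral flag to contact the participant about device use. Keep the detail with sponsor device support. Suspected device deficiencies and adverse events must still reach those who act on them through the existing reporting route (Section 14).
3. Have missing ratings solicited with a fixed script by existing staff who do not receive device-use flags. The missing-rating notice that triggers the call stays. Mark phone-obtained ratings in the database and add to 7.8.5 a repeat of the primary analysis without them, stating how those attacks enter the 50% denominator.

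The cost is a change to alert routing, two deletions, a short call script, one database field and one sensitivity analysis, with no change to sample size. A site that relies on one coordinator would have to name a second existing staff member for the calls. The main downside is that the coordinator sees less detail when a participant misuses the device.
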